5.5.1 Visit 1: 24-48 hours after removal of peripheral nerve block catheter

Subjects will be assessed at least 24-48 hours after removal of the peripheral nerve catheter (or after the effects of a single shot femoral and/or sciatic nerve block have worn off). They will be evaluated for post-surgical complications, and for the presence of phantom limb sensation or pain and RLP. Average pain severity and anatomic distribution will be reported by answering BPI-SF #2 and #5.

Subjects in Group 1 will proceed to Visit 2 and undergo placement of the peripheral nerve stimulator lead(s) by post-op day 7, in addition to receiving SMT. Subjects in Group 2 will skip to Visit 3. They will be treated with SMT and followed up by study investigators daily until discharged. They will subsequently be followed up by telephone according to the Schedule of Study Procedures.

5.5.2 Visit 2A: Placement of percutaneous peripheral stimulator leads (Group 1

only)

Subjects randomized to Group 1 proceed to placement of the stimulator leads by post-op day 7 to begin peripheral nerve stimulation therapy with the SPRINTTM PNS System (Figure 2.1). The procedure for placement of the peripheral nerve stimulator lead (Figure 2.2) is similar to placement of a peripheral nerve catheter for local anesthetic blockade. The main difference is that instead of delivering medications, electrical stimulation is applied to the peripheral nerve over a wide range of parameters. Also, the stimulator lead does not need to be placed as close to the nerve as a local anesthetic peripheral nerve catheter. This study will evaluate the application of one or two leads per subject: one for the femoral nerve and/or one for the sciatic nerve. Lead placement is expected to take up to 2 hours.

Figure 3. Example of a percutaneous anterior approach that may be used to access the femoral nerve. The inguinal crease (noted with dotted line), femoral artery (noted with an "A"), and needle insertion site (noted with a circled "X") are shown on the right leg.

[figure not shown]

Figure 4. Cross section shows the femoral nerve (FN), femoral artery (FA), and femoral vein (FV) relative to surrounding structures of adipose tissue and muscle (e.g. sartorius muscle, iliopsoas muscle, and pectineus muscle; and the white dashed-line box indicates the area scanned in the ultrasound image in Figure 6.

Figure 5. Needle insertion using out of plane ultrasound guidance (ultrasound transducer is perpendicular to the needle) is shown but in plane ultrasound guidance may also be used.

[figure not shown]

Figure 6. Ultrasound image shows the FN (at the bottom right tip of the white line) relative to the FA, FV, and the iliopsoas muscle (IPM) (adapted from Ultrasound for Regional Anesthesia).

Adapted from SPR TherapeuticsTM

329

330

331 332

333

Lead placement near the sciatic nerve uses the posterior transgluteal or subgluteal approaches that are commonly practiced in regional anesthesiology. Landmarks for the transgluteal approach include the greater trochanter and the posterior superior iliac spine. The subject is placed in lateral decubitus position, and the lead introducer is aimed approximately 4 cm distal to the midpoint between the greater trochanter and the posterior iliac spine to target the sciatic nerve. Landmarks for the subgluteal region include the

Figure 7. Example of a percutaneous posterior approach that may be used to access the sciatic nerve. The dashed line bisecting the line between the greater trochanter (GT) and ischial tuberosity (IT) indicates the sciatic nerve and the midpoint ("x") marks the needle insertion location

[figure not shown]

Figure 8. Cross section shows the sciatic nerve (arrowhead) surrounded by the gluteus maximus muscle (GMM), quadratus femoris muscle (QFM), adipose tissue, IT, and GT.

Figure 9. The ultrasound probe is placed perpendicular to the sciatic nerve to provide a transverse image as the needle is inserted.

[figure not shown]

Figure 10. Ultrasound image shows the sciatic nerve (arrowhead) relative to surrounding structures (adapted from Ultrasound for Regional Anesthesia).

Adapted from SPR TherapeuticsTM

336

337

338 339

340

341 342

343

344

345

346

334

335

Alternate anatomic approaches for lead placement (e.g. popliteal approach for sciatic nerve) may be utilized to optimize safety and improve patient response. Once a lead has been placed, stimulus parameters will be adjusted to determine the settings necessary to evoke comfortable sensations that overlap with the regions of pain associated with TFA or TTA surgery. Parameters which can be adjusted include amplitude (mA), duration (μ s), and frequency (Hz). Study staff will attempt to determine the parameters which produce the most comfort as endorsed by the subject. These parameters will vary from subject to subject and may be adjusted as needed throughout the study.

Once satisfactory lead placement and stimulus parameters have been achieved, subjects will begin the 30 to 60-day treatment phase. Subjects will be provided with a manual and educated on the use and care of the device. Stimulation may be delivered continuously up to 24 hours per day until the end of therapy.

- Leads will be indwelling no more than a total of 60 days. If a lead is dislodged or broken prior to the end of therapy, the subject may be offered the opportunity for a lead replacement depending on their willingness to undergo the lead replacement procedure and time remaining in the treatment period.
- If the subject provides media consent, photographs and video of the lead placement procedure may be recorded and are intended for potential use in publications, future grant applications, and educational purposes. Media may be stored on VA CAC access computers on a HIPAA-compliant share drive.

5.5.3 Visit 2B: Daily hospital evaluations until discharge

Subjects in both groups will be evaluated by study investigators daily until they are discharged. The length of stay is approximately 14 days for TFA per VASQIP 2016 quarter 4 data (Veterans Affairs Surgical Quality Improvement Program). Based on this data, subjects in Group 1 will likely be discharged 7 to 14 days after starting peripheral nerve stimulation. Group 1 subjects will be asked questions to re-assess the stimulation-evoked paresthesia coverage of the leg. Stimulator devices will be inspected to ensure appropriate function. Lead exit sites are inspected for skin irritation, infection, and inflammation. These risks will be minimized by using sterile leads and sterile technique. Maintenance, care of the leads and lead exit sites, and bandage changes will be performed as needed. Subjects in both groups will be evaluated for the presence of phantom sensations, as well as least, worst, and average PLP or RLP according to the Schedule of Study Procedures.

364 .

5.5.4 Visits 3, 4 and 5: Weekly telephone follow-up evaluations

Visits 3, 4 and 5 consist of weekly telephone evaluations at 1, 2 and 3 weeks after starting peripheral nerve stimulation (Group 1) or discontinuation of peripheral nerve block (Group 2). If issues related to the peripheral nerve stimulator device or leads occur and cannot be resolved by telephone, subjects may be evaluated in the Interventional Pain Clinic as needed.

Subjects are asked to rate their worst, least, and average PLP and RLP (BPI #3, #4, and #5). A medical reconciliation will be completed during each phone evaluation by asking the subject how many pills of narcotic pain medications they have left and querying the Virginia Prescription Monitoring Program Database.

5.5.5 Visit 6: First outpatient clinic evaluation / 30 days after start of PNS

All subjects are asked to return to the Interventional Pain Clinic at 4 weeks after the start of peripheral nerve stimulation. Stimulator devices (Group 1) will be inspected to ensure appropriate function. Lead exit sites are inspected for skin irritation, infection, and inflammation. Maintenance, care of the leads and lead exit sites, and bandage changes will be performed as needed.

All subjects are asked to rate their worst, least, and average PLP and RLP (BPI #3, #4, and #5). Subjects will rate the degree with which pain has interfered with general activity, mood, walking ability, sleep, and enjoyment of life (BPI #9). Pain Disability Index (PDI) and Patient Global Impression of Change (PGIC) will be assessed. A medical reconciliation will be completed during each phone evaluation by asking the subject how many pills of narcotic pain medications they have left and querying the Virginia Prescription Monitoring Program Database.

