5.4.2 Exclusion Criteria

- 231 Exclusion criteria are systemic infection, immunosuppressive disorder, implanted electronic devices,
- pregnancy, previous allergy to skin contact materials and/or anesthetic agent altered mental status, inability
- 233 to provide consent, greater than 180 morphine equivalents (MED) per day.

234 5.5 Study Plan

- The study includes 13 Visits. Please refer to the Appendix for a schedule of study procedures for both
- 236 groups as well as outcomes measured at each visit.
- Patients planned for nontraumatic TFA or TTA will be screened by the study investigators who are working
- on the Acute Pain Service (APS). APS is usually consulted for all transferoral and transtibial amputations
- 239 to provide perioperative anesthesia, which typically includes placement of a peripheral nerve catheter for
- local anesthetic blockade. When a potential subject is identified, study investigators will begin a chart
- review for screening purposes. The investigators will review the medical record of potential subjects and
- complete Form 00 (Screening and Demographic Information). Chart review will include the collection of
- name, social security number and date of birth from CPRS, the ORC, and the Vascular Clinic. Protected
- Health Information (PHI) will be used to locate and review appropriate medical records (CPRS and paper
- medical records) to determine study eligibility. If a subject appears to meet all eligibility criteria (see
- 245 incident records) to determine study engionity. If a subject appears to ineet an engionity enterta (see
- Section 5.4. Eligibility), then he/she will be contacted by study investigators and given recruitment
- 247 materials detailing study objectives, randomization, procedures, follow-up encounters, assessments, and
- 248 potential risks and benefits. The subject will be provided with patient information pertaining to the
- 249 peripheral nerve stimulator system under investigation. If permitted by the subject, a sponsor representative
- or their designee may be present at any of the study visits to advise on material handling and answer
- questions as needed.

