Patients who are interested in participation will be asked to complete a Beck Depression Inventory (see Form BDI) to be screened for depression (must score 20 or less) prior to enrollment. Veteran participants who are evaluated by study staff and suspected to be depressed will be further evaluated by a psychiatrist or psychologist utilizing the Mental Health Consultation and Liaison Service at McGuire VAMC. Research study staff will page the C&L service at [name] (Use [name] after 4pm and on weekends) and then walk the participant to the C&L provider to facilitate the evaluation on the day that the participant

presents as depressed. If non-veterans participants are enrolled, arrangements made for him/her to be evaluated at a non-VA facility.

[figure not shown]

Figure 1 Subject flowchart.

258

259

260261

Patients who agree to participate in the study will be asked to sign the Consent Form. Ideally, patients should provide informed consent and be enrolled in the study prior to surgery. Typically, the local anesthetic peripheral nerve block catheters (or single shock femoral or sciatic nerve blockade) are placed on the day prior to surgery or day of surgery. Subjects will be given the opportunity to enroll in the study when the catheter is placed, however, those who wish to decide on enrollment after their surgery may be enrolled up until the time in which their peripheral nerve block catheter is removed, which is usually by post-op day 5. Upon enrollment, subjects will be evaluated by APS daily.

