5.5.6 Visit 7, 8, and 9: Weekly follow-up telephone evaluations

Visits 7, 8, and 9 consist of weekly telephone evaluations at 5, 6, 7 weeks after starting peripheral nerve stimulation (Group 1) or discontinuation of peripheral nerve block (Group 2). If issues related to the

peripheral nerve stimulator device or leads occur that cannot be resolved by telephone, subjects may be evaluated in the Interventional Pain Clinic if needed.

Subjects are asked to rate their worst, least, and average PLP and RLP (BPI #3, #4, and #5). A medical reconciliation will be completed during each phone evaluation by asking the subject how many pills of narcotic pain medications they have left and querying the Virginia Prescription Monitoring Program Database.

5.5.7 Visit 10: Second outpatient clinic evaluation / up to 60 days after start of PNS

All subjects are asked to return to the Interventional Pain Clinic at approximately 60 days after starting peripheral nerve stimulation (Group 1) or discontinuation of peripheral nerve block (Group 2). Stimulator leads will be removed by gentle traction. The lead will be visually inspected by study staff to evaluate for lead fracture. In the case of a retained lead fragment, study staff will determine the most appropriate medical plan to further evaluate and treat the subject. In most instances, retained lead fragments do not need to be removed and are rarely associated with further complications. Lead exit sites are inspected for skin irritation, infection, and inflammation. Both groups will continue to be treated with SMT as needed until the end of participation in the study. Subjects in Group 1 are encouraged to complete the entire 60-days of peripheral nerve stimulation, however are free to discontinue treatment at any time during the treatment phase.

5.5.8 Visits 11, 12, and 13: Phone evaluations at 3, 6, and 12 months after study enrollment

Telephone evaluations for both groups occur at approximately 3, 6, and 12 months after study enrollment. Outcome measures to be assessed are listed in the Schedule of Study Procedures.

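### Follow-up visits through Visit 10 run on different clocks in the two groups, so Group 1 is assessed slightly later after surgery than Group 2

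*Combined protocol and SAP*

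**What the plan says.** - Visits 3-5 (section 5.5.4) take place "1, 2 and 3 weeks after starting peripheral nerve stimulation (Group 1) or discontinuation of peripheral nerve block (Group 2". Section 5.5.6 applies the same two origins to Visits 7-9 at 5, 6 and 7 weeks. Section 5.5.7 sets Visit 10 at about "60 days after starting peripheral nerve stimulation (Group 1) or discontinuation of peripheral nerve block (Group 2".
- Visit 6 (section 5.5.5) has one origin: "All subjects are asked to return to the Interventional Pain Clinic at 4 weeks after the start of peripheral nerve stimulation". The Appendix schedule also labels it by weeks of PNS.
- Section 5.5.1 fixes the order of events. "Subjects will be assessed at least 24-48 hours after removal of the peripheral nerve catheter", or once a single-shot block has worn off. Group 1 then goes on to "placement of the peripheral nerve stimulator lead(s) by post-op day 7".
- Section 5.5 allows enrollment until the "peripheral nerve block catheter is removed, which is usually by post-op day 5". It describes perioperative anesthesia "which typically includes placement of a peripheral nerve catheter for" local anesthetic blockade, and the inclusion criteria in section 5.4.1 do not require a block.
- Section 5.5.3 covers the inpatient period: "Subjects in both groups will be evaluated by study investigators daily until they are discharged". Section 5.5.8 times Visits 11-13 from enrollment in both groups.
- Section 6.3 averages pain over the first and second months after surgery and compares groups by post-operative phase, using a two-sample t-test. No visit windows and no adjustment for days since surgery are given.

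**The concern.** The two origins are different events, and their order is fixed: block removal, then Visit 1, then PNS. The visit rule therefore makes time since surgery depend on the assigned group, always in the same sense, while section 6.3 analyzes by time since surgery. If pain changes over these weeks, part of any difference at a same-numbered visit reflects when the question was asked. The outcomes exposed are worst, least and average pain at Visits 3-10, interference, PDI and PGIC at Visit 6, and FIM at the 4- and 8-week clinic visits.

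There is also a practical gap. As written, Visit 6 has no date for Group 2, and a Group 2 subject with no block has no origin for any visit from 3 to 10.

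Section 6.1 says that the results will be used to refine assessment procedures for a larger trial. If that trial copied this schedule, the offset would stay the same while the standard error shrank.

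**Working it through.** The plan gives no figure for this offset, so there is none to reproduce.

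**Inputs from the protocol.** Catheter usually out by post-op day (POD) 5 (section 5.5); Visit 1 at least 24-48 hours later and leads placed by POD 7 (section 5.5.1); 8 subjects per group (section 6.1); two-sample t-test (section 6.3).

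**Assumed, because the documents do not give them.** Linear change in pain of 0.25-1.0 points per week (the upper value is plausible only early after surgery); SD 2-3 points; two-sided 5% level; 30-day months; block-end days earlier than POD 5.

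**Step 1: lag.** Lag = POD of PNS start − POD of block end.
- Usual pathway: 6 − 5 = 1 day; 7 − 5 = 2 days.
- Block ends on POD 3, PNS on POD 7: 7 − 3 = 4 days.
- Single-shot block worn off on POD 1, PNS on POD 7: 7 − 1 = 6 days.
- An early block end alone is not enough: block off on POD 1 with PNS on POD 2 gives 1 day.

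**Step 2: visit days.** POD of visit = origin + nominal interval. Group 2's Visit 6 is taken as 4 weeks after block end.

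| Visit | Group 1 (PNS on POD 7) | Group 2 (block off POD 5) |
|---|---|---|
| 3 | 14 | 12 |
| 5 | 28 | 26 |
| 6 | 35 | 33 |
| 9 | 56 | 54 |
| 10 (60 days) | 67 | 65 |

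With a 1- or 2-day lag, no visit falls in a different month in the two groups. With a 4-day lag, Visit 10 counted at 8 weeks falls on POD 63 against POD 59, on either side of day 60. With a 6-day lag, Visit 6 falls on POD 35 against POD 29, on either side of day 30.

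**Step 3: shift at one visit.** Shift = lag × weekly slope / 7.
- 1 day at 0.25: 1 × 0.25/7 = 0.04 points.
- 2 days at 1.0: 2 × 1.0/7 = 0.29 points.
- 6 days at 1.0: 6 × 1.0/7 = 0.86 points.

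**Step 4: against the pilot's precision.** SE = SD × √(2/8), which is 1.0 for SD 2 and 1.5 for SD 3. Rejection with no treatment effect comes from the noncentral t distribution with 14 df and noncentrality shift/SE.

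| Shift | Case | SD 2 | SD 3 |
|---|---|---|---|
| 0.04 | 1 day, 0.25/week | 5.0% | 5.0% |
| 0.29 | 2 days, 1.0/week | 5.8% | 5.4% |
| 0.86 | 6 days, 1.0/week | 12.6% | 8.3% |

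**Step 5: monthly means.** Section 6.3 does not say whether daily inpatient scores enter the first-month mean. Suppose they do, with one score per day from POD 1 to POD 14 and then Visits 4 and 5. For a 2-day lag, the mean assessment day is (105 + 21 + 28)/16 = 9.625 in Group 1 and (105 + 19 + 26)/16 = 9.375 in Group 2. The difference is 0.25 day, or 0.009-0.036 points. If only Visits 3-5 count, the shift equals the single-visit figure. The second-month mean rests on Visits 6-9, so it carries the full single-visit shift: at 2 days, 0.07 points at 0.25/week and 0.29 at 1.0/week.

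**The case against.** The strongest reply is that the usual lag is 1-2 days in a 16-subject feasibility study with unadjusted p-values, where even the upper single-visit shift of 0.29 points is small beside a standard error of 1.0-1.5. That stands for the usual pathway. It is not shown for early or single-shot blocks when PNS waits until POD 7.

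Other parts of the reply also stand, and they rule out stronger readings that a reader might infer:

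- *Visit 6 cannot be dated for Group 2.* Group 2's Visits 5 and 7 fall 3 and 5 weeks after block discontinuation, so 4 weeks is clearly implied. This is probably a drafting omission.
- *Single-shot blocks have no counterpart to catheter removal.* Section 5.5.1 already treats wear-off as the counterpart, though only for Visit 1. The later visit sections do not repeat it. Only a subject with no block has no origin at all, and section 2.1 calls catheter-based analgesia essential to standard therapy at this site.
- *The schedule favors PNS.* That needs pain to be falling. The documents give no trajectory, and section 2.1 notes that many patients' worst postoperative pain comes after discharge, in which case the shift could go the other way.
- *The chronic-pain comparison is compromised.* Visits 11-13 share one clock, and inpatient scores can be compared on the same post-op day.

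Finally, counting from PNS start has a rationale. It fixes stimulation exposure at each Group 1 visit, and section 4.2.2 defines PGIC as change since treatment began. A common clock trades some of that away.

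**Conclusion.** The point holds as a minor design flaw. Through Visit 10 the scheduling rule builds in an avoidable group difference in time since surgery, on an analysis that is itself indexed by time since surgery. In the usual pathway the lag is 1-2 days and the shift 0.04-0.29 points at a single visit, with null rejection of 5.0-5.8%. If the block ends early or is single-shot and PNS still starts on POD 7, the lag can reach about 6 days, the shift 0.86 points and null rejection about 12.6%. That upper figure needs the steepest assumed slope and the smaller assumed SD. The lags follow from the protocol's sequence; the slopes, SDs, significance level and early block-end days are assumptions. The sign of the shift cannot be determined from the documents. Nothing here threatens the feasibility aim.

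**What to change.** Count the outcome assessments at Visits 3-10 in both groups from one origin that every subject has. Two would serve: the surgery date, which section 6.3 already uses, or Visit 1, which both groups attend before any lead is placed. Use the same target days and windows in each group and include Visits 6 and 10 explicitly. In the same edit:

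- Record post-op day at every assessment, and days of stimulation in Group 1.
- Keep the PGIC reference point as stated, and define it for Group 2.
- Reconcile 4 weeks with 30 days for Visit 6, and 8 weeks with about 60 days for Visit 10.
- State in section 6.3 whether daily inpatient scores enter the first-month mean.

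Leave PNS duration and lead-removal timing as the protocol states them.

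The cost is protocol wording, a visit calculator and one or two case report form fields, with no added patients. There are two downsides. Group 1 assessments will no longer fall at exact whole weeks of stimulation, which is why days of stimulation should be recorded. If lead removal and the Visit 10 assessment fall on different days, an extra contact may be needed; FIM then stays at the clinic visit with its post-op day recorded, so a small timing difference may remain for that measure.

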5.5.6 Visit 7, 8, and 9: Weekly follow-up telephone evaluations

Visits 7, 8, and 9 consist of weekly telephone evaluations at 5, 6, 7 weeks after starting peripheral nerve stimulation (Group 1) or discontinuation of peripheral nerve block (Group 2). If issues related to the

peripheral nerve stimulator device or leads occur that cannot be resolved by telephone, subjects may be evaluated in the Interventional Pain Clinic if needed.

Subjects are asked to rate their worst, least, and average PLP and RLP (BPI #3, #4, and #5). A medical reconciliation will be completed during each phone evaluation by asking the subject how many pills of narcotic pain medications they have left and querying the Virginia Prescription Monitoring Program Database.

5.5.7 Visit 10: Second outpatient clinic evaluation / up to 60 days after start of PNS

All subjects are asked to return to the Interventional Pain Clinic at approximately 60 days after starting peripheral nerve stimulation (Group 1) or discontinuation of peripheral nerve block (Group 2). Stimulator leads will be removed by gentle traction. The lead will be visually inspected by study staff to evaluate for lead fracture. In the case of a retained lead fragment, study staff will determine the most appropriate medical plan to further evaluate and treat the subject. In most instances, retained lead fragments do not need to be removed and are rarely associated with further complications. Lead exit sites are inspected for skin irritation, infection, and inflammation. Both groups will continue to be treated with SMT as needed until the end of participation in the study. Subjects in Group 1 are encouraged to complete the entire 60-days of peripheral nerve stimulation, however are free to discontinue treatment at any time during the treatment phase.

5.5.8 Visits 11, 12, and 13: Phone evaluations at 3, 6, and 12 months after study enrollment

Telephone evaluations for both groups occur at approximately 3, 6, and 12 months after study enrollment. Outcome measures to be assessed are listed in the Schedule of Study Procedures.

